Time to relapse defined as admission to hospital, crisis house or crisis resolution team for mental health related problems. Data for this outcome were obtained from the informatics department of the relevant Trusts. This was in the form of the date of admission and which service admitted in the 18 months following baseline. Those that did not have any data recorded were assumed to not have any admissions and their data were censored 18 months after entry into the trial. If a participant died within the follow up period, the study team had this information and follow up will be censored at the date of death if they have did have a relapse before then. Likewise if their drop out date was known, this will be used as the date of censoring. Everything possible was done to trace people who dropped out to ensure that it was ascertained whether they had a relapse and if so when. This is because

drop out may be related to the outcome and therefore introducing informative censoring. [outcome type: time to event]

Secondary Outcomes

Secondary outcomes were measured at 12 weeks and 18 months. Analysis will be separately at these time points to match the clinical question of examining the outcomes at each of these time points rather than over time.

Cannabis positive urine sample at follow up. This will be a dichotomous outcome, positive versus negative.

Positive symptom score using the positive scale of the Positive and Negative Syndrome Scale (PANSS)⁹. This consists of seven items: Delusions, Conceptual disorganization, Hallucinatory behaviour, Excitement, Grandiosity, Suspiciousness and Hostility. Each item is scored on a scale from one to seven with one indicating absent and seven indicating extreme. These are summed to give an overall score which ranges from 7 to 49. [outcome type: continuous]

Negative symptom score using the negative scale of the PANSS. This consists of seven items: Blunted affect, Emotional withdrawal, Poor rapport, Passive-aphathetic social withdrawal, Difficulty in abstract thinking, Lack of spontaneity and flow of conversation, Stereotyped thinking. Each item is scored on a scale from one to seven with one indicating absent and seven indicating extreme. These are summed to give an overall score which ranges from 7 to 49. [outcome type: continuous]

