Social functioning, based on self-reports regarding engagement in work or study, defined as any work (including sheltered or voluntary) or study (full or part time). [outcome type: dichotomous]

Number of days cannabis is used in the previous 12 weeks for follow up at 12 weeks and previous six months for 18 month follow up [outcome type: count]

Number of admissions over 18 months follow up. The primary analysis of this outcome will be operationalised to include those who provided a full 18 months follow up and those who died during follow up [outcome type: dependent on number of events. It may be possible to use this as count data else it will be dichotomised to none versus any]

Data collection

Data were collected at three time points, baseline, 12 weeks and 18 months post baseline.

Baseline

Demographic and social information (age, gender, ethnicity, social standing, living arrangements, employment, benefits received)

Clinical characteristics

Cannabis use using Time Line Follow Back¹⁰

Part E of the Structured Clinical Interview for DSM IV¹¹

Urine sample results

The Positive and Negative syndrome scales (PANSS)⁹

Employment status using questions from the Client Service Receipt Inventory (CSRI)

SF-12 (to be used in health economic analysis)^{13, 14}

EQ-5D (to be used in health economic analysis)

CSRI tailored to the study¹³ (primarily for health economic analysis)

12 weeks and 18 months

Urine sample results

Positive and Negative Syndrome Scale (PANSS)⁹
Engagement in work or study from the CSRI
SF-12 (to be used in health economic analysis)^{13,14}
EQ-5D (to be used in health economic analysis)
CSRI (to be used in health economic analysis)

18 months

Date of admission to hospital or crisis resolution team

Data entry

Data were entered using a web based system set up by Sealed Envelope⁸. This was set up so that, it mirrored the data collection sheets in order. It also had range checks, consistency checks and for closed questions gave a number of options plus “other” where appropriate. Assessors who entered the data will had no access to the group allocation through this system.

Data were checked by the statistician and health economists before analysis and any problems reported to the Trial Manager, who will rectify them as appropriate before data analysis.

Statistical analyses

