The CONSORT¹⁻³ flow diagram will be constructed by/in collaboration with the Trial Manager who will have logs of service users who do and do not agree to take part in the study. It will include number of service users randomised to each arm of the trial, and the numbers who have follow up data available.

All analyses will be on an intention to treat basis and data from the pilot trial will be incorporated into the main trial.

Data will be analysed using Stata version 14¹⁵.

Descriptive statistics

Initial analyses will look at summary statistics for all variables, both overall and by randomised group. Summary statistics for continuous variables will be mean, median, SD, lower quartile, upper quartile, minimum and maximum and reported appropriately according to distribution. Summary statistics for categorical variables will be frequency and percentage within each category.

Summary statistics of baseline variables by whether a participant has dropped out of the study will also be examined to determine whether the drop outs had similar characteristics to those who remained in the study at baseline.

Analysis of the primary outcome

The primary outcome will be initially examined using Kaplan Meier survival curves by randomised allocation. If the assumptions of proportional hazards is satisfied, Cox Proportional Hazards modelling to compare the intervention and control groups will be carried out, adjusting for severity of cannabis use at baseline (the stratification variable, dichotomous – 1 to 3 times a week versus 4+ times a week) and whether the participant was part of the pilot trial. If the assumption of proportional hazards is not fulfilled, alternative modelling strategies will be employed. Robust standard errors will be used to account for clustering by therapist; which should account for most of the centre effects in this multicentre individually randomised trial. Hazard ratios and 95% confidence intervals will be presented.

Analysis of the secondary outcomes

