These will be analysed separately for data collected at 12 weeks and 18 months. Models will include severity of cannabis use at baseline and whether the participant was part of the pilot trial. For the dichotomous outcomes (cannabis positive urine, engaged in work or study), logistic regression with robust standard errors to account for clustering by therapist will be used. If there are too few participants engaged in work or study for logistic regression to be possible then results will be reported descriptively. For continuous outcomes (positive and negative symptoms), linear regression with robust standard errors will be used.

For count outcomes, Poisson regression with robust standard errors will be used for count outcomes (number of cannabis days and number of admissions over follow up). If there are excess zeros for either count outcome, then the use of zero inflated Poisson regression will be explored.

Appropriate estimates and 95% confidence intervals will be presented for all analyses.

Missing data

There is not much missing data for the primary outcome since it is an objective outcome collected from the appropriate informatics departments.

There is missing data for other variables, especially at follow up. This may be because of non-attendance at the follow up appointment or non-response to specific questions. The extent and patterns of missingness will be assessed. Potential predictors of missing values that are related to the outcomes will be identified. .

Multiple imputation¹⁶ may be used if it is felt to be necessary. We will only impute outcome data if surrogate outcomes or variables closely related to the missing outcome(s) are available. Otherwise there is no gain in imputing outcomes¹⁷.

The primary analysis will be complete case analysis with analysis using multiple imputation being a supportive analysis if it is carried out.

Supportive analyses

There will be up to six supportive analyses for the primary outcome:

1. Analysis of all outcomes with their baseline predictors of missingness, that is modelling including the randomised allocation, whether the participant was in the pilot trial and the level of cannabis use at baseline

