2. Analysis of the primary outcome excluding those participants who have no follow up secondary outcome data (for 12 weeks and 18 months separately) because those who drop out or die may be different to those who remain in the study and/ or survive. Before doing this, some demographic statistics comparing those who remained in the study and those who dropped out will be produced.
3. Analysis of those in the main trial only as some changes were made to the protocol at the end of the pilot before the main trial commenced, which might mean the participants behave differently to those in the pilot trial.
4. Analysis of the primary outcome controlling for the same factors as in the primary analysis plus the number of psychoeducation sessions attended (which is being offered in both arms of the trial).
5. Analysis of the primary outcome controlling for the same factors as the primary analysis and number of admissions in the six months prior to baseline.

6. Analysis of the primary outcome controlling for the same factors as the primary analysis, but using centre as the clustering variable not therapist.

There will be up to two supportive analyses for the number of admissions during follow up:

1. In addition to the factors included in the main analysis, this will include predictors of missingness.

2. Including those who were discharged within 18 months and assuming they had no admissions over the follow up time.

There may be supportive analyses for secondary outcomes collected at 18 months, as outlined in the missing data section.

Exploratory analysis:

We will investigate potential patterns and degree of non-compliance using clinical definitions of compliance and descriptive analysis. We will perform a Complier Average Causal Effect (CACE) analysis if feasible.

There are no subgroup analyses planned.

Health Economic analyses

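### The main analysis of number of admissions keeps only 18-month completers and deaths, with no exposure term, and so discards admissions recorded before discharge or drop-out

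*SAP*

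**What the plan says.** **Analysis set.** Under Secondary Outcomes, the primary analysis of number of admissions is "operationalised to include those who provided a full 18 months follow up and those who died during follow up". On the outcome type, the SAP adds: "It may be possible to use this as count data else it will be dichotomised to none versus any".

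**Model.** Under Analysis of the secondary outcomes: "Poisson regression with robust standard errors will be used for count outcomes (number of cannabis days and number of admissions over follow up". A zero-inflated version is to be explored if there are excess zeros. On covariates: "Models will include severity of cannabis use at baseline and whether the participant was part of the pilot trial". Neither follow-up time nor an offset is named.

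**Principles.** Under Statistical analyses: "All analyses will be on an intention to treat basis". Under Missing data: "The primary analysis will be complete case analysis with analysis using multiple imputation being a supportive analysis if it is carried out".

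**Supportive analyses of admissions.** There are up to two. The first adds predictors of missingness to the model. The second is described as "Including those who were discharged within 18 months and assuming they had no admissions over the follow up time".

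**Data held.** Under Primary Outcome, admissions come from Trust informatics departments: "This was in the form of the date of admission and which service admitted in the 18 months following baseline". The same section censors time to relapse at death, and at drop-out where that date is known. It also warns that drop-out may be informative.

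**The concern.** Whether a participant completes 18 months is decided after randomisation. An analysis set defined by completion can differ between arms even when the arms were balanced at entry. Discharge may well depend on how a person is doing, and the SAP itself accepts that drop-out may be related to outcome.

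The restriction also wastes data. A participant discharged at month 12 with two recorded admissions contributes both to the trial's database but nothing to this analysis. For time to relapse, the same person's first admission is used.

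The second supportive analysis does not fill the gap. Read literally, it replaces that person's two admissions by none and treats the six unobserved months as event-free. It also covers only those who were discharged, not those lost for other reasons.

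At stake are the precision of this secondary comparison and, if exit differs between arms, its direction.

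**Working it through.** **1. Figures in the SAP.** It states no admission rate, discharge rate or number of deaths, so there is no figure for this outcome to reproduce. The sample size supplies two inputs:
- 460 × 1.06 = 487.6, rounded to 488. Then 488/0.9 = 542.2, or 543 against the stated 544. The chain reproduces to within rounding.
- At the planned 10% drop-out, 0.10 × 544 = 54.4, so about 54 participants would leave the main admissions analysis.

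Everything below rests on assumed rates.

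**2. Data discarded.** Measure time in units of 18 months.
- *Exit at a constant hazard of 0.105.* Completers are exp(−0.105) = 0.900. Mean observed time is (1 − 0.900)/0.105 = 0.949. Share of person-time discarded: (0.949 − 0.900)/0.949 = 5.2%. By simulation (0.9 admissions per 18 months, gamma frailty with variance 1), about 5% of admissions are discarded if exit is unrelated to risk, and about 7% if higher-risk people leave more often.
- *Exit uniform over months 3 to 18.* Mean observed time among leavers is 10.5/18 = 0.583. At 10% exit: 0.0583/0.9583 = 6.1%. At 20%: 0.1167/0.9167 = 12.7%.

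**3. Precision.** Assume 272 per arm, mean 0.9, gamma heterogeneity with shape 0.8, and 20% leaving at random, uniformly over months 3 to 18.
- Completers: variance of a count is 0.9 + 0.81/0.8 = 1.9125. The SE of the log rate ratio is √[2 × 1.9125/(272 × 0.8 × 0.81)] = 0.147.
- All participants with an offset: E[t] = 0.9167 and E[t²] = 0.8 + 0.2 × 0.398 = 0.8796. Mean variance is 0.9 × 0.9167 + (0.81/0.8) × 0.8796 = 1.7156. The SE is √[2 × 1.7156/(272 × 0.825²)] = 0.136.
- Simulation gives 0.147 and 0.135. From the closed forms, the offset analysis carries (0.1473/0.1361)² = 1.17 times the information.

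**4. Bias when the true rate ratio is 1.**

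| Assumed exit | Completers | Offset, all participants | Discharged set to zero |
|---|---|---|---|
| About 10% in both arms, unrelated to risk | 1.00 | 1.00 | – |
| About 10% in both arms, same relation to risk | 1.00 | 1.00 | – |
| About 5% v 14%, same relation to risk | 1.05 | 1.02 | – |
| About 10% in both arms, related to risk in one arm only | 1.11 | 1.05 | – |
| About 15% v 5%, higher-risk people leave more | 0.91 | 0.95 | – |
| 15% v 5%, lower-risk people leave more | 1.06 | 1.02 | 0.95 |
| 30% v 15%, lower-risk people leave more | 1.12 | 1.04 | 0.92 |

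The first five rows use frailty variance 1 and exponential exit times. The last two use shape 0.8 and uniform exit times. A dash means not computed. The offset removes about half of the completer bias or more, but not all of it.

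**5. Deaths without an offset.** If deaths have on average half the exposure, the rate ratio shifts by the factor (1 − 0.5d₁)/(1 − 0.5d₀), where d is the proportion dying in each arm. For 3% v 0% this is 0.985. For 5% v 2% it is 0.975/0.990 = 0.985. The shift is about 1.5%.

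**The case against.** Several stronger readings are tempting, and the SAP does not support them.

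- *The outcome is analysed only in completers and deaths.* This is true of the main analysis, not of the plan. Two supportive analyses follow, and one brings discharged participants back.
- *Intention to treat is broken.* Participants stay in their randomised arms, and the SAP openly declares a complete-case approach. What stands is that not everyone randomised is included and the two statements are not reconciled. Complete case is also an awkward label here, because those left out have recorded admissions and person-time. Only the remainder is missing.
- *Deaths are wrongly counted as full exposure.* The SAP does not say so; it is inferred from the missing offset. Admissions up to death within a fixed 18 months is a recognised quantity, and the effect is small (step 5). What is missing is a statement of which quantity is meant.
- *An offset cures everything.* It does not: step 4 shows residual bias wherever exit is informative and differs between arms.
- *The completer and assume-none analyses together tell the reader nothing.* In the two scenarios where both were computed, they fall on either side of the truth, so they do inform sensitivity. Neither is a good main estimate.

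It can also fairly be said that the 20% and 30% scenarios exceed the SAP's only planning figure of 10%. An exposure time may not exist for everyone, since drop-out dates are used only where known. The SAP also does not say that discharge ends record coverage. These points limit the size of the concern and shape the remedy, but they do not justify discarding recorded admissions.

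**Conclusion.** The point holds for the main analysis of number of admissions. As written, the rule selects on a post-randomisation event and leaves out recorded events that the trial uses elsewhere. The supportive analysis meant to address this would, read literally, overwrite admissions recorded before discharge.

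The loss of data follows from the rule whenever anyone with some coverage leaves early: about 5 to 7% of admissions at 10% exit and about 13% at 20%. Bias is conditional. There is none if exit is unrelated to risk, or equally common and equally related to risk in both arms. It reaches roughly 10% in the rate ratio at overall exit near 10% if the arms differ, and 12% in the heavier 30% v 15% case. The SAP offers no evidence that they differ. All of these figures rest on assumed admission rates, heterogeneity and exit patterns.

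This is one secondary outcome. The primary outcome and the sample size are unaffected. The change is worth making because it is cheap and most of the dates are already held.

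**What to change.** **Main analysis.** Include all randomised participants with any record coverage. Count admissions from randomisation to the earliest of: discharge or transfer out (where this ends coverage), known drop-out date, death, or 18 months. Fit the planned Poisson model with therapist-clustered robust standard errors and log(time at risk) as offset. Carry the offset into any zero-inflated model.

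**Unknown drop-out dates.** Apply the Primary Outcome rule, so that both outcomes treat these people alike, and say that this assumes no unrecorded admissions up to 18 months.

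**Dichotomised version.** If the outcome becomes none versus any, allow for follow-up time there too; a Poisson offset alone does not cover that case.

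**Deaths.** State whether the target is a rate while alive or a count over a fixed 18 months. The offset as proposed gives the former.

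**Supportive analyses.** Keep the completer-plus-deaths analysis as supportive. In the analysis of discharged participants, retain admissions recorded before discharge and assume none only afterwards.

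**Wording.** Add a sentence reconciling the intention-to-treat and complete-case statements for this outcome.

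**Cost.** A short paragraph of SAP text, one derived exposure variable, and a check with the Trusts on whether discharge ends coverage. The offset assumes a constant admission rate over observed time, and it reduces but does not remove bias from informative discharge.

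### The main analysis of number of admissions is limited to participants with a full 18 months of follow-up plus deaths, a post-randomisation selection that can bias the rate ratio if leaving differs by arm

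*SAP*

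**What the plan says.** Four parts of the SAP bear on this endpoint.

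- **Secondary Outcomes.** The main analysis is "operationalised to include those who provided a full 18 months follow up and those who died during follow up". On the type of outcome, the SAP adds: "It may be possible to use this as count data else it will be dichotomised to none versus any".
- **Analysis of the secondary outcomes.** The model is given as "Poisson regression with robust standard errors will be used for count outcomes (number of cannabis days and number of admissions over follow up"). No exposure time or offset is stated.
- **Statistical analyses.** The general principle is "All analyses will be on an intention to treat basis". The section Missing data then makes complete case the primary approach.
- **Supportive analyses.** Up to two are allowed for this endpoint. The first adds predictors of missingness to the model. The second is "Including those who were discharged within 18 months and assuming they had no admissions over the follow up time".

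The primary outcome is handled differently. Under Primary Outcome, the SAP says of its source: "Data for this outcome were obtained from the informatics department of the relevant Trusts". It continues: "This was in the form of the date of admission and which service admitted in the 18 months following baseline". Someone who leaves early stays in the analysis: "Likewise if their drop out date was known, this will be used as the date of censoring". The same section warns that drop-out may be related to the outcome and so make the censoring informative.

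**The concern.** Whether a person is still under follow-up at 18 months is settled after randomisation, and may depend on both the arm and how well the person is. The second supportive analysis shows that people discharged within 18 months are outside the main set. If the intervention kept people well and they were discharged sooner, its low-admission participants would be removed and its effect understated. The opposite pattern would overstate it.

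The two relapse-related endpoints would also rest on different people. Someone admitted in month 2 who drops out in month 10 is an event in the Cox model but is absent from the admissions count. The SAP gives no reason for treating the two endpoints differently.

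**Working it through.** **Plan's own figure.** There is none to reproduce. The SAP states no admission rate, no share with under 18 months and no target effect for this endpoint. Its 10% drop-out allowance and total of 544 belong to time to relapse.

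**Who is used in each analysis**

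| Participant | Time to relapse | Admissions, main | Admissions, supportive 2 |
|---|---|---|---|
| Full 18 months | kept | kept | kept |
| Died | kept, censored at death | kept, no time term | kept |
| Drop-out, date known | kept, censored at that date | excluded | not mentioned |
| Discharged within 18 months | no separate rule | excluded | added with zero admissions |

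Supportive analysis 1 adds covariates; nothing in the SAP says that it brings excluded people back.

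**Illustration (all inputs assumed)**

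- Each person's relative admission risk f is gamma with mean 1 and variance 1.
- A share L of the arm leaves early, with probability proportional to exp(−b·f), so low-risk people leave more often; b runs from 0.3 (weak link) to 2 (strong link).
- Leaving time is uniform over months 3 to 18, a mean of 10.5/18 = 0.583 of the period.
- The true rate ratio is 1.00.

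Leavers then have mean risk 1/(1+b). Relative to the whole arm:

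- SAP set: mean = [1 − L/(1+b)] / (1 − L)
- All observed time with offset: rate = [1 − 0.417·L/(1+b)] / (1 − 0.417·L), where 0.417 = 1 − 0.583

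Worked case: b = 2, control L = 0.15, intervention L = 0.25.

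- SAP set: control 0.950/0.85 = 1.118; intervention 0.917/0.75 = 1.222; ratio 1.09.
- Offset: control 0.979/0.9375 = 1.044; intervention 0.965/0.896 = 1.078; ratio 1.03.

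| Leaving, control v intervention | SAP set, b = 0.3 to 2 | Offset, b = 0.3 to 2 |
|---|---|---|
| 10% v 10% | 1.00 | 1.00 |
| 8% v 12% | 1.01 to 1.03 | 1.00 to 1.01 |
| 15% v 25% | 1.03 to 1.09 | 1.01 to 1.03 |
| 25% v 15% | 0.97 to 0.91 | 0.99 to 0.97 |

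Simulation with mean 0.8 admissions per 18 months agreed with these formulas. Runs with other link strengths gave 1.04 to 1.10 for the SAP set at 15% v 25%, and 1.01 to 1.04 with the offset.

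**Counting leavers as zero (supportive 2).** The arm mean becomes 1 − L/(1+b). At 15% v 25% the ratio is 0.808/0.885 = 0.91 for b = 0.3 and 0.917/0.950 = 0.96 for b = 2. In this model it errs in the opposite direction to the main analysis.

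**Discarded events.** With mean 0.8 admissions, the share of control leavers admitted before leaving is 1 − [(1+b)/0.667]·ln[(1.8+b)/(1.133+b)]. That is 26% for b = 0.3 and 13% for b = 2.

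**Deaths.** If 2% of one arm die at mid-follow-up, that arm loses 2% × 0.5 = 1% of its time at risk. Without an offset the ratio moves by about 1%.

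**The case against.** **Size.** The strongest reply is that the bias may be trivial. The SAP's only drop-out figure is 10%, and Missing data says that little is missing for the routine-data primary outcome. Both statements concern the primary outcome, so they are only a guide here, but nothing supports a 10-point gap between arms. Sampling error is also much larger than the bias. With mean 0.8, frailty variance 1 and 272 per arm (544/2), the variance of a count is 0.8 + 0.64 = 1.44. The standard error of the log ratio is then √(2 × 1.44/0.64/272) = 0.13, so the 95% interval spans a factor of about 1.29 either way. This stands as a limit on size. It is not a reason to prefer the restricted set.

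**Openly declared.** The SAP says that complete case is primary, so its intention-to-treat line is loosely worded rather than secretly broken. Supportive analysis 1 can also correct selection explained by the added covariates. Both points are fair, but that analysis is optional and does not use partial follow-up.

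**Data source.** A reader might infer that the Trusts hold recorded admissions for the excluded people and that the SAP knowingly drops them. The SAP names the Trust extract for the primary outcome only. That the count uses the same records is a reasonable inference, and no number of affected people is given.

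**Deaths.** Counting admissions to 18 months or death is a recognised estimand, so keeping deaths without an offset is defensible. This part is minor.

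**Conclusion.** The inclusion rule is a real weakness in one secondary endpoint and should be changed. That the set is chosen after randomisation, and does not match either the intention-to-treat statement or the primary outcome's handling of partial follow-up, follows from the text alone. The loss of admissions before leaving depends on the count coming from the dated Trust records.

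The bias is conditional. It needs leaving to differ by arm in amount or in its link to admission risk, and its direction cannot be known from the SAP. On the assumed inputs it is a few percent for a 4-point gap in leaving and up to about 10% for a 10-point gap.

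A reader might infer that the admissions result will be badly biased. Main-set ratios up to 1.32 can be produced, but only by assuming that 20% leave in each arm, with high-risk people leaving in control and low-risk people in intervention. Nothing in the SAP supports that pattern.

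**What to change.** Replace the inclusion rule under Secondary Outcomes with wording such as:

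> All randomised participants with admission data are analysed. Admissions are counted from randomisation to the earliest of 18 months, death, or the known date of drop-out or end of ascertainment, using the same censoring rules as the primary outcome. Discharge ends observation only if Trust ascertainment stops then. Poisson regression with robust standard errors is used, with log(observed time) as offset. The set with a full 18 months of follow-up is a supportive analysis.

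The SAP should also state the source of the count and report, by arm, how many participants have under 18 months and why.

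**Cost.** This is a wording change and one model option. Death and known drop-out dates are already used for the primary outcome. Whether dates for the end of Trust ascertainment exist needs checking, because the SAP mentions none.

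**Downsides.** The offset reduces bias from informative leaving but does not remove it. The estimate becomes a rate over observed time. The offset does not help the none-versus-any fallback, which needs its own rule for unequal follow-up.
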